We will use dual energy x-ray absorptiometry (DXA) scans to measure BMD annually at 3 anatomical sites (lumbar spine, total hip, and wrist). Additionally, we will derive the trabecular bone score (TBS), an index of lumbar spine trabecular microarchitecture.

Hypothesis: Relative to women using DMPA only (without tenofovir exposure) and women using PrEP only (without DMPA exposure), women concurrently using TDF-based PrEP and DMPA will have lower bone mass and more disruptions in bone microarchitecture.

2. We will investigate whether young women concurrently using TDF-based PrEP and DMPA experience: 1) higher rates of bone turnover, a direct precursor to bone loss and 2) subclinical kidney injury and hypoestrogenism, markers of two mechanistic pathways between TDF and DMPA use and bone mass

At baseline, 3, 6, 12, and 24 months, we will measure:

- 1) Markers of bone formation and resorption (e.g. NTX, P1NP, serum intact parathyroid hormone, total and bioavailable 25-OH-vitamin D)
- 2) Markers of kidney function (phosphate, glucose, creatinine, total protein, albumin) and
- 3) Markers of estrogen (serum estradiol, sex hormone binding protein, and the occurrence of amenorrhea)

Hypothesis: Relative to women using DMPA only and PrEP only, women concurrently using TDF-based PrEP and DMPA will have increased bone turnover markers and PTH. In addition, women concurrently using TDF-based PrEP and DMPA will have more frequent subclinical kidney injury (relative to women without tenofovir exposure) and reduced serum estrogen (relative to women without DMPA exposure).

3. Using mediation analysis, we will identify the degree to which the pathways through subclinical kidney injury and hypoestrogenism account for changes in bone density among women concurrently using TDF-based PrEP and DMPA

We will conduct mediation analysis to determine the degree to which changes in the pathways through subclinical kidney injury, hypoestrogenism and the combination of these pathways account for changes in bone density.

Hypothesis: The pathway through hypoestrogenism will be a stronger link between concurrent TDF-based PrEP and DMPA use and bone density changes.

Population

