- Current or recent history of primary or secondary amenorrhea
- Taking medications known to interfere with bone metabolism (steroids, anti-convulsants, bisphosphonates, cancer drugs).
- Has any other condition that would preclude the ability to provide informed consent, make study participation unsafe, complicate the interpretation of study findings or otherwise interfere with achievement of the study objectives, in the investigator's discretion.

Sample size and study power

Power calculations are based on the number of participants needed to achieve aim 1. Our target sample size is 500 women, of which 300 will be using DMPA and 200 will be using condoms for contraception. We calculate that with 300 women newly initiating DMPA and 75% of women choosing to initiate PrEP, thus with 225 women concurrently using PrEP and DMPA and 75 women using DMPA without PrEP, we will have >90% power to detect changes as low as 2.2% in BMD (with 1.0 g/cm² mean BMD loss) at any anatomical site between women using PrEP and DMPA concurrently and women using DMPA only during the 24 month follow up period (Table 4). Should more than 90% of women choose to initiate PrEP (270 women concurrently using PrEP and DMPA and 30 women using DMPA without PrEP), we will have 80% power to detect changes of >2.7% or more and should initiation rates be closer to 50% (150 women concurrently using DMPA and PrEP and 150 women using DMPA without PrEP), we will have >90% power for all comparisons.

Table 4. Power calculations. N=500: 300 on DMPA and 200 on condoms, shown with a range of PrEP acceptance for the primary comparison of DMPA + PrEP vs DMPA ($\alpha=0.05$)

Expected PrEP acceptance	Outcome: BMD (Aim 1)			Outcome: NTX (Aim 2)		
	Mean % Δ (std dev range)	Mean Δ	Power	Mean % Δ	Mean Δ	Power
75% (225 DMPA+PrEP, 75 DMPA)	2.2 (4–5) (0.5–1.0)	0.5 (0.5–1.0)	91%	2.2 (4–5)	0.10 (0.2 – 0.5)	>99%
75% (225 DMPA+PrEP, 75 DMPA)	2.5 (4–5) (0.5–1.0)	0.5 (0.5–1.0)	>96%	2.5 (4–5)	0.20 (0.2 – 0.5)	>96%
75% (225 DMPA+PrEP, 75 DMPA)	3 (4–5) (0.5–1.0)	1.0 (0.5–1.0)	>99%	3 (4–5)	0.50 (0.2 – 0.5)	>99%
90% (270 DMPA+PrEP, 30 PrEP)	2.5 (4–5) (0.5–1.0)	0.5 (0.5–1.0)	74-90%	2.5 (4–5)	0.10 (0.2 – 0.5)	>99%

Recruitment

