Women will initiate contraception at the study clinic or a family planning clinic, as they are seeking services. Throughout study follow up, the study will assume responsibility for contraceptive provision, including DMPA injections, and care of all other methods desired by women. The staff at the IDI-Kasangati research clinic have extensive experience with the provision of contraception and contraceptive counseling during previous HIV prevention studies.

PrEP provision and adherence monitoring

Co-formulated emtricitabine (FTC)-TDF (Truvada®) will be provided as PrEP by the study through donation from Gilead Sciences, LLC. PrEP counseling and provision will follow WHO guidelines, or Ugandan clinical guidelines when they are available.⁶⁰ We will measure adherence using three different methods:

1. Pill counts will be conducted by the pharmacist during study visits to determine the percentage of expected pills that were used
2. Real time monitoring will be conducted using an electronic monitoring system that captures a date-time stamp each time the pill container is opened
3. The primary circulating form of TDF, tenofovir (TFV), will be quantified in blood archives from 1) a random sample of up to 15% of women who initiate PrEP to characterize the adherence in the cohort overall and 2) a targeted group of women who have no BMD change and women who experience a fracture

Laboratory processing to measure markers of bone turnover, subclinical kidney injury, and hypoestrogenism

Using state-of-the-art assay techniques on archival samples, we will measure 1) established markers of bone turnover and bone health, 2) markers of subclinical kidney injury, and 3) markers of hypoestrogenism (Table 5). Archived samples will be batch-analyzed.

Table 5. Measurements for markers of bone turnover, subclinical kidney injury, and hypoestrogenism

Outcome	Biomarkers	Primary Outcome definition	Secondary Outcome definition
Bone turnover and bone health	NTX, P1NP	Percent change from baseline in NTX and P1NP	Percent change from baseline in serum levels of: 
 intact PTH vitamin D binding protein, 25-(OH) vitamin D

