The primary analysis will be separate comparisons of the annualized rates of change in BMD and TBS of the spine and hip between women using PrEP and DMPA concurrently versus women using DMPA only (comparison 1), women using PrEP only (comparison 2), and women using neither (comparison 3). Analyses will account for baseline BMD.

Aim 2, part 1. We will investigate whether young women concurrently using TDF-based PrEP and DMPA experience higher rates of bone turnover relative to women using either agent singly or neither agent

This outcome will be defined by the percent change from baseline of serum levels of NTX and P1NP over 24 months. Secondary outcomes will include: 1) percent change from baseline in serum levels of intact PTH, total 25-(OH)D, bioavailable (i.e. unbound or free) 25-(OH)D calculated from vitamin D binding protein (VDBP) using the standard equation.

$$\text{Free 25(OH)D} = \frac{\text{total 25(OH)D}}{1 + (6 \times 10^3 \times \text{albumin}) + (7 \times 10^8 \times \text{DBP})}$$

To test the hypothesis that combined PrEP and DMPA use is associated with greater bone turnover than DMPA use alone, we will use time-dependent linear mixed-effects regression models to compare mean percent changes in NTX and P1NP between concurrent users of PrEP and DMPA versus users of DMPA only. Secondary powered comparisons will be between: a) concurrent users of PrEP and DMPA versus users of PrEP only; b) users of PrEP only versus users of condoms only; c) users of DMPA only vs users of condoms only. Analysis of the percent change from baseline in serum levels of intact PTH, total 25-OH-D and bioavailable 25-OH-D over 24 months will follow a similar approach. All analyses will be adjusted for confounders and we will consider a broad range of demographic, medical, lifestyle, and sexual behavior characteristics as potential confounders.

Aim 2, part 2. We will investigate whether young women concurrently using TDF-based PrEP and DMPA experience elevated markers of subclinical kidney injury relative to women using TDF-based PrEP alone

This outcome will be defined as having either:

- 1) eGFR decline ($\geq 25\%$ decline from baseline or creatinine clearance $< 60 \text{ mL/min}$). GFR will be calculated using the Chronic Kidney Disease Epidemiology (CKDE) collaboration equation

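### Table 4's >99% power for NTX in rows 1 and 4 does not follow from its printed inputs, which give 91–98% and 74–90% on the planned percent-change scale

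*Protocol*

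**What the plan says.** Table 4, in the protocol's section Sample size and study power ("Table 4. Power calculations. N=500: 300 on DMPA and 200 on condoms"), covers the comparison of DMPA plus PrEP with DMPA alone at alpha 0.05. It has a BMD block for Aim 1 and an NTX block for Aim 2.

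- Rows 1 to 3 are labelled "75% (225 DMPA+PrEP, 75 DMPA". The NTX inputs are 2.2%, 2.5% and 3% (SD 4–5), with absolute changes of 0.10, 0.20 and 0.50 (SD 0.2–0.5). The stated NTX powers are >99%, >96% and >99%.
- Row 4 is labelled "90% (270 DMPA+PrEP, 30 PrEP". The NTX inputs are 2.5% (SD 4–5) and 0.10 (SD 0.2–0.5). The stated NTX power is >99%.
- The BMD block prints the same percent differences and SDs row by row, with powers of 91%, >96%, >99% and 74–90%.

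The text above the table describes the row 4 scenario differently from its label: "270 women concurrently using PrEP and DMPA and 30 women using DMPA without PrEP".

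The NTX outcome is on the percent scale. Table 5 defines it as "Percent change from baseline in NTX and P1NP", and Section V, Aim 2, part 1 will "compare mean percent changes in NTX and P1NP between concurrent users of PrEP and DMPA versus users of DMPA only".

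**The concern.** Three features of the table cannot all be right.

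1. Rows 1 and 4 carry identical group sizes, percent differences and SDs for BMD and NTX, yet the powers differ: 91% against >99% in row 1, and 74–90% against >99% in row 4.
2. From row 1 to row 2 the groups and SDs stay the same and the NTX effect grows on both scales, yet the stated power falls from >99% to >96%.
3. Row 4 has row 2's percent difference and half its absolute difference, with 30 comparators instead of 75, yet a higher stated power.

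NTX is a primary outcome for bone turnover. If the printed power is believed, a null NTX result at high PrEP uptake would seem to exclude the assumed difference more firmly than the design allows.

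**Working it through.** **Inputs (all from Table 4).** Groups are 225 vs 75 and 270 vs 30. Differences and SDs are as listed above. Alpha is 0.05; the protocol does not give the sidedness, and two-sided is assumed because it reproduces the BMD column.

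**Formula.** Power ≈ Φ(δ / (SD × √(1/n₁ + 1/n₂)) − 1.96). The square root is √(1/225 + 1/75) = 0.1333 for rows 1–3 and √(1/270 + 1/30) = 0.1925 for row 4. The powers tabulated below use the noncentral t distribution and lie within about 0.3 points of this approximation.

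**Percent scale.** Each cell shows δ divided by its standard error, then the power.

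| Row | Difference | SD 4 | SD 5 | Printed BMD | Printed NTX |
|---|---|---|---|---|---|
| 1 | 2.2 | 4.13 → 98.4% | 3.30 → 90.8% | 91% | >99% |
| 2 | 2.5 | 4.69 → 99.7% | 3.75 → 96.2% | >96% | >96% |
| 3 | 3.0 | 5.63 → >99.9% | 4.50 → 99.4% | >99% | >99% |
| 4 | 2.5 | 3.25 → 89.9% | 2.60 → 73.6% | 74–90% | >99% |

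The whole BMD column is reproduced. So is the text's 80% for 2.7% at 270 vs 30: 2.7 / (5 × 0.1925) = 2.81, power 79.9%. NTX rows 2 and 3 agree as well. NTX rows 1 and 4 do not.

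**Absolute scale.**

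| Row | Difference | SD 0.2 | SD 0.5 | Printed NTX |
|---|---|---|---|---|
| 1 | 0.10 | 3.75 → 96.2% | 1.50 → 32.1% | >99% |
| 2 | 0.20 | 7.50 → >99.9% | 3.00 → 84.9% | >96% |
| 3 | 0.50 | >99.9% | >99.9% | >99% |
| 4 | 0.10 | 2.60 → 73.6% | 1.04 → 17.8% | >99% |

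**What >99% would need.** The largest SD giving 99% power is δ / (√(1/n₁ + 1/n₂) × (1.960 + 2.326)).

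- Row 1, percent: 2.2 / (0.1333 × 4.286) = 3.85 (3.84 with t).
- Row 4, percent: 2.5 / (0.1925 × 4.286) = 3.03 (3.02 with t).
- Absolute scale: about 0.17 (row 1) and 0.12 (row 4).

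All four lie below the printed SD ranges. Equivalently, the difference detectable with 99% power at SD 4–5 is 2.3–2.9% at 225 vs 75 and 3.3–4.1% at 270 vs 30.

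**One-sided 0.05.** Row 1 becomes 95.0–99.3% and row 4 82.8–94.5%, so >99% still does not hold across the SD range. BMD row 1 at SD 5 would become 95.0% and no longer match the printed 91%.

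**Repeated measures.** Averaging four follow-up values with common correlation ρ multiplies the SD by √((1 + 3ρ)/4). To exceed 99% on the percent scale, ρ must be no more than about:

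- row 1: 0.45 at SD 5, 0.89 at SD 4;
- row 4: 0.15 at SD 5, 0.43 at SD 4.

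At an assumed ρ of 0.5 and SD 5, rows 1, 2 and 4 reach 98.7%, 99.7% and 90.8% (normal approximation). On the absolute scale at SD 0.5, even ρ = 0 gives only 85% in row 1 and 55% in row 4.

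**The case against.** The strongest defence is the planned analysis. For Aim 2 the protocol states "At baseline, 3, 6, 12, and 24 months, we will measure", which gives four follow-up values for a mixed model, while BMD has only two follow-up scans. Higher power for NTX than for BMD from equal inputs is therefore not absurd in itself. But Table 4 prints no correlation, and row 4 at SD 5 would need a very low one. Nor can one method give row 1 more than 99% and row 2 only just over 96%, because row 2 has the larger effect in the same groups.

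A second reading is that the NTX powers were computed on the absolute scale at SD 0.2 and the row 1 and row 2 cells were exchanged: 0.10 gives 96.2% and 0.20 gives >99.9%. This explains rows 1–3 about as well at that end of the SD range, so the source of the error is not certain. Row 1 would still be misprinted, row 2 would be as well, and row 4 would still be 73.6%.

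A third point is that the table's layout is visibly disturbed in the available text, so the percent inputs shared by BMD and NTX might come from merged cells. That weakens the BMD–NTX comparison but not the finding, because the absolute NTX inputs fail too.

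Four limits stand. At SD 4, row 1 falls short by less than one point. The BMD column matches on the percent scale only: an absolute change of 0.5 with SD 0.5–1.0 at 225 vs 75 gives 96% or more, not 91%. The sample size rests on Aim 1, and row 4 is a contingency scenario. A null NTX result should in any case be judged by its confidence interval.

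**Conclusion.** The >99% NTX power in rows 1 and 4 is wrong as printed. On the planned percent-change scale, row 1 is 91–98% and row 4 is 74–90%. The row 1 shortfall is about 8 points at SD 5; the row 4 shortfall is 9 to 25 points. The chance of missing the assumed difference, stated as under 1%, is 2–9% at 75% uptake and 10–26% at 90% uptake.

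This rests on a two-sided 0.05 two-sample comparison with the printed SDs and no loss to follow-up, the same basis that reproduces the percent-scale BMD column. The row 4 comparator label is a separate, smaller error that the text above the table already contradicts. This should be fixed, but it does not affect the Aim 1 power entries or the target of 500 women.

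**What to change.** Restate the NTX power column on the percent-change scale, to match Table 5 and the Aim 2 analysis: 91–98%, 96 to >99%, >99% and 74–90% for rows 1 to 4. Name the test, the sidedness and the SD behind each figure.

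If >99% came from a repeated-measures calculation, print the number of samples and the assumed correlation, and recompute all four rows with them. If the absolute-change inputs are kept, the corresponding powers are 32–96%, 85 to >99%, >99% and 18–74%.

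Change the row 4 comparator label to 30 women using DMPA without PrEP.

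The cost is a change to the table and text only. The stated Aim 2 power becomes less favourable; recruitment and sample size do not change.

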The primary objective of this study is to address critical safety questions with concurrent TDF-based PrEP and DMPA use. We hypothesize that young women using TDF-based PrEP and DMPA will have lower bone acquisition and altered bone metabolism. Bone mineral metabolism is in part regulated by the kidney, and we hypothesize that bone effects from concurrent PrEP and DMPA use will be driven by subclinical kidney injury, a known side effect of TDF, as well as DMPA-induced hypoestrogenism. To investigate our hypothesis, we will enroll a prospective cohort of approximately 500 HIV-uninfected women ages 16-25 years in Kampala, Uganda who have substantial HIV risk and are initiating DMPA or barrier method contraception. Over a 24-month period, we will offer TDF-based PrEP. We will use state-of-the-art radiologic, biochemical, and epidemiologic methods to test the hypothesis that concurrent TDF-based PrEP and DMPA use results in compounding adverse effects on bone health.

II. BACKGROUND

PrEP as a novel HIV prevention strategy for women

Women in sub-Saharan Africa are disproportionately affected by HIV and the greatest rates of HIV incidence are among women below age 25. In Uganda, 4% of young women were estimated to be living with HIV and 140,000 people became infected in 2013.¹ For women with substantial HIV risk, tenofovir disoproxil fumarate (TDF)-based pre-exposure prophylaxis (PrEP) is a daily oral medication highly protective against HIV acquisition.²⁻⁷ Randomized trials of PrEP efficacy demonstrated high HIV protection at levels >90% in analyses of participants with high adherence.⁴⁻⁷ Recent landmark approvals of TDF-based PrEP in sub-Saharan Africa and commitment from large-scale funding partners (including PEPFAR) will accelerate its roll-out.⁸ WHO antiretroviral guidelines now include PrEP and clinical guidelines for Uganda are under development. A key advantage of PrEP for women is that it does not require the cooperation of a male partner, a challenging characteristic of condom use. Although two trials of PrEP conducted with African women showed null results, there is substantial objective evidence indicating that these studies were limited by low adherence to study medication.^{3, 9, 10} Concerns about PrEP adherence by young women have been abated by data from PrEP delivery studies demonstrating very high adherence with open-label products with known efficacy and accompanied by risk-related counseling.¹¹

Unintended consequences of PrEP

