Recruitment strategies will include collaboration with local family planning clinics, gynecologists, women's health clinics, HIV counseling and testing centers, and public and private health clinics. Additionally, we will conduct outreach activities during community markets to recruit women newly initiating contraception. Recruitment materials will educate women about the benefits and potential adverse effects of contraceptives and PrEP, based on available data.

General study procedures

Over a 24-month period, we will follow women quarterly with HIV rapid testing, PrEP adherence counseling and refills, DMPA injections, and provision of other contraceptives as desired. At enrollment and quarterly visits, we will assess physical activity, sexual behavior, and menstrual cycle characteristics. Annually, we will conduct physical exams and anthropometric readings. Sexually transmitted infections will be routinely assessed syndromically, according to national guidelines. Women will be encouraged to consider their HIV risk and fertility desires at every visit and counseled about contraception and PrEP accordingly. Dual energy x-ray absorptiometry (DXA) scans will be performed at baseline and annually thereafter. Blood and urine samples will be obtained quarterly, aliquoted, and archived at minus 80° Celsius.

DXA and TBS assessments

DXA scans will be conducted at study enrollment (within 1 week of contraceptive initiation if possible), 12, and 24 months after enrollment. DXA is the clinical standard for measuring BMD. It is painless and non-invasive. Women will be exposed to a relatively low level of radiation which is <1/10 the dose of a standard chest x-ray, and less than a day's exposure to natural radiation. BMD by DXA of the hip and spine is generally considered the most reliable way to classify osteoporosis, assess changes in BMD, and predict fracture risk. We will measure areal BMD of the lumbar spine (L1-4), hip, whole body and body composition (total and % fat and lean mass) using a DXA machine. For the TBS analysis, no additional image acquisition is required. TBS will be performed as a re-analysis of the lumbar spine taken as part of the standard DXA procedure with specialized software.

Contraceptive provision

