We expect that some women who stop using contraception will become pregnant. Women who become pregnant while using PrEP will be counseled about the known and unknown risks and benefits of PrEP use during pregnancy, in accordance with U.S. CDC and WHO guidelines.^{60, 61} Women who are pregnant will not undergo DXA scans, and their DXA scans will be postponed until their pregnancy is complete.

Visit-specific procedural tables

	SCR	ENR	M1	M3 & M15	M6 & M18	M9 & M21	M12 & M24 & EXIT
ADMINISTRATIVE & REGULATORY PROCEDURES							
Obtain informed consent	X	X					
Collect/update locator information	X	X	X	X	X	X	X
Collect/update demographic information	X	X					X
CLINICAL & COUNSELING PROCEDURES							
HIV pre and post-test counseling	X	X	X	X	X	X	X
Risk reduction counseling & condom provision	X	X	X	X	X	X	X
Contraceptive counseling		X	X	X	X	X	X
Contraceptive provision			[X]	X	X	X	X
PrEP counseling, including adherence counseling	X	X	X	X	X	X	X
PrEP provision		X	X	X	X	X	X
PrEP pill count			X	X	X	X	X
Physical exam		X	X	[X]	[X]	[X]	X
Anthropometric readings		X					X
DXA scan (unless pregnant)		X					X
Syndromic management of STIs	X	X	X	X	X	X	X
LABORATORY PROCEDURES							
Creatinine testing when using PrEP	X				X (M6 only)		X
HBV surface antigen	X						
HIV rapid test (EIA testing and HIV RNA quantification, if rapid test positive)	X	X	X	X	X	X	X
Urine pregnancy test	X	X	X	X	X	X	X
Collect urine specimen for archive		X		X	X	X	X
Collect blood specimen for archive		X		X	X	X	X
CLINICAL & BEHAVIORAL DATA COLLECTION							
Medical history questionnaire, including occurrence of fractures	X	X	X	X	X	X	X
Sexual behavior & contraceptive use questionnaire		X	X	X	X	X	X
Physical activity & dietary questionnaire		X		X	X	X	X

Menstrual cycle questionnaire	X	X		X	X	X	X
X required procedure; [X] if clinically indicated							

Safety monitoring

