Kidney function will be monitored 6 months after initiation and annually thereafter, in accordance with Ugandan guidelines, using creatinine clearance calculated by Cockroft–Gault equation. DXA scans will be reviewed in real time and women with bone density below -2.0 standard deviation of the z-score will be referred locally for vitamin D assessment and provided with any necessary therapy. The investigators will be responsible for continuous close monitoring of all adverse events that occur among study participants. For the purposes of this study, only serious adverse events (SAEs) and adverse events felt related to PrEP will be documented on case report forms. Adverse events and the severity of clinical symptoms will be scored using the DAIDS Table for Grading the Severity of Adult and Pediatric AEs.⁶² The study safety monitor will review clinical and laboratory SAEs in real time as they are reported by the site clinicians on CRFs and through email within 48 hours of occurrence. As needed, the safety monitor will work provide rapid consultation with clinicians regarding the management of toxicities. A Safety Review Team comprised of the study investigators and lead clinicians will review clinical and laboratory safety reports summarizing SAEs via conference call on an approximately quarterly basis.

IV. DATA COLLECTION

Clinical data including anthropometric, dietary, physical activity and other lifestyle and sexual behaviors, will be recorded electronically on case report forms (CRFs) and data will be uploaded to a secure server. Automated legal range checks will be programmed to reduce data entry errors and internal quality control reports will be run on a monthly basis. Results from laboratory testing will be returned to the data center at the University of Washington and stored alongside other key study data. DXA scan images will be downloaded to project-specific databases and sent to the University of Washington via secure file transfer system. TBS measurements will be performed using the lumbar spine DXA images. PrEP adherence data from the electronic monitoring device will be stored on an encrypted website and downloaded to the University of Washington server on a regular basis.

V. DATA ANALYSIS

Aim 1. We will assess whether young women using TDF-based PrEP and DMPA concurrently attain lower peak bone mass over a 24-month period and have evidence of disrupted microarchitecture, relative to women using either agent singly or neither agent

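### The visit table fixes creatinine tests by study month, so some women who start PrEP after enrolment have no listed kidney check at the 6 months the safety text requires

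*Protocol*

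**What the plan says.** **Safety text.** Protocol section III, Safety monitoring: "Kidney function will be monitored 6 months after initiation and annually thereafter, in accordance with Ugandan guidelines". The section does not define *initiation*.

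**Visit table.** In Visit-specific procedural tables, the row "Creatinine testing when using PrEP" has entries at screening, in the shared M6/M18 column (restricted to M6), and in the M12/M24/exit column. The cells for M3/M15 and M9/M21 are empty. The key reads "X required procedure; [X] if clinically indicated", and the creatinine row carries neither mark at M9, M15, M18 or M21. No footnote moves the test to the date of PrEP start.

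**When PrEP can start.** The opening summary states: "Over a 24-month period, we will offer TDF-based PrEP". General study procedures adds: "Women will be encouraged to consider their HIV risk and fertility desires at every visit and counseled about contraception and PrEP accordingly". The table marks PrEP provision at every visit from enrolment onward.

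**Other relevant text.** Under PrEP provision and adherence monitoring: "PrEP counseling and provision will follow WHO guidelines, or Ugandan clinical guidelines when they are available". The row "Collect blood specimen for archive" is marked at enrolment and at every quarterly visit, but under Laboratory processing, "Archived samples will be batch-analyzed".

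**The concern.** The safety rule counts time from an event in the individual woman, and the table counts time from enrolment. These coincide only when PrEP starts at enrolment. A site working from the table would test some later starters on a schedule that the safety text does not allow.

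What is at stake is the timing of a real-time kidney check on a drug whose renal effect is one of the protocol's own concerns. The Background section says it is unknown whether the small eGFR decline worsens with prolonged use or in women of small body mass. The archived blood does not fill the gap, because it is assayed in batches and gives no timely result for clinical care.

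**Working it through.** **Inputs.**
- Rule: a check 6 months after initiation (Safety monitoring), taken as PrEP initiation because the table row applies only during PrEP use.
- Listed creatinine visits after screening: M6, M12, M24 (visit table).
- Possible scheduled start visits s: 0 (enrolment), 1, 3, 6, 9, 12, 15, 18, 21, from the PrEP provision row.
- A test on the day of starting is a baseline value and does not count as a check after start.
- The woman stays to M24. An earlier exit visit also carries a creatinine test.

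**Formulas.** Due visit = s + 6. First wait = smallest (t − s) over listed t > s. Excess = first wait − 6.

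**The plan's own figure.** For s = 0 the due visit is M6, M6 is listed, and the first wait is 6 − 0 = 6 months. The table reproduces the rule for a start at enrolment.

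**All start visits.**

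| Start | Due | Listed checks, months after start | First wait | Excess | Test listed at due visit? |
|---|---|---|---|---|---|
| M0 | M6 | 6, 12, 24 | 6 | 0 | yes |
| M1 | M7 | 5, 11, 23 | 5 | −1 | no (no visit at M7) |
| M3 | M9 | 3, 9, 21 | 3 | −3 | no |
| M6 | M12 | 6, 18 | 6 | 0 | yes |
| M9 | M15 | 3, 15 | 3 | −3 | no |
| M12 | M18 | 12 | 12 | +6 | no |
| M15 | M21 | 9 | 9 | +3 | no |
| M18 | M24 | 6 | 6 | 0 | yes |
| M21 | M27 | 3 | 3 | −3 | no (after follow-up ends) |

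**Reading A: a check at or before 6 months meets the rule.** The first wait exceeds 6 months at 2 of 9 start visits: M12 by 6 months and M15 by 3 months.

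**Reading B: the check must fall at 6 months.** Four start visits have a quarterly visit on the due date but no creatinine listed there: M3, M9, M12 and M15. The widest interval under this reading, apart from the M12 case, is for M9 starters, who are checked at 3 months and then not until 15. M1 and M21 starters have no study visit on their due date; their first listed checks come at 5 and 3 months.

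**After the fix.** Tests are added at M9 (start M3), M15 (start M9), M18 (start M12) and M21 (start M15). Starts at M6 and M18 already have their 6-month test. First waits become 6, 5, 3, 6, 3, 6, 6, 6, 3. The longest falls from 12 to 6 months, and every start visit whose due date is a scheduled visit has a test there.

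**The case against.** The strongest reply is that text and table can be read together. The table sets out the calendar for the participant the protocol mainly describes, who starts PrEP and DMPA together at enrolment. The safety text, which follows the table directly, supplies the rule for anyone else. The table does not forbid an extra test, does not claim to override the text, and is itself conditional on PrEP use. A site that applied the text would add the missing test. The protocol also defers to national and WHO guidelines, whose timing for later starters is not given here.

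Most of that stands, and it is why the point is small. But the key presents the table as the list of required procedures, and the one entry that could cover M18 is expressly limited to M6. Where two instructions on a safety test differ, the protocol should say which one governs. The pointer to guidelines does not supply the missing entries.

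A second reply is that late starts are only inferred. No passage describes a woman starting at M12 or M15, the provision marks may largely be refills, and the power section treats uptake as a single proportion. This also stands as a limit on size: the number affected could be zero. It does not remove the conflict, because PrEP is offered and counselled on throughout follow-up.

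A reader might also infer that the table breaks the annual part of the rule even for enrolment starters, since a year after the 6-month check is M18. The text does not say whether the yearly checks count from that check or from initiation. Counted from initiation they fall at M12 and M24, as listed, so this reading is not established.

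**Conclusion.** The conflict is real and minor. The table fits women who start PrEP at enrolment, but not all later starters. The first listed check is late for starts at M12 (12 months) and M15 (9 months) if an earlier check is accepted as meeting the rule. On the literal wording, starts at M3 and M9 also lack a 6-month check. The count of two start visits therefore depends on a choice that the protocol does not make, and it should not be given without that condition.

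The conclusion assumes that *initiation* means PrEP initiation and that a same-day test is a baseline. The 12- and 9-month waits are maxima, since an exit before M24 would bring the check forward.

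Two stronger readings are not supported. A reader might infer that a sizeable group goes a year without kidney monitoring, but the protocol gives no number of late starters, and a site that follows the safety text would test on time. A reader might also infer damage to the kidney outcome in Aim 2, but Aim 2 uses markers measured in archived samples at baseline, 3, 6, 12 and 24 months, not the real-time safety test. Power and Aims 1 to 3 are unaffected.

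**What to change.** Keep every creatinine test now listed and add one footnote to the creatinine row, in words such as: *For women who start PrEP after enrolment, creatinine is also tested at the quarterly visit 6 months after PrEP start (e.g. M18 for a start at M12, M21 for a start at M15); see Safety monitoring.* In Safety monitoring, state that *initiation* means PrEP initiation.

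The cost is at most one extra creatinine test per later starter: one for starts at M3, M9, M12 and M15, and none for starts at M6 and M18, where the test is already listed. Each added test falls at an existing quarterly visit (M9, M15, M18 or M21) with a required blood draw, so no visit is added. M15 starters would be tested at M21 and again at M24, 3 months apart, which is the only near-duplication at the end of follow-up. Women who start at enrolment have no added tests.
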